5.1.3 Reporting of serious adverse events

Investigators and other site personnel will inform the FDA, via a Medwatch form, of any unexpected and possibly study drug related SAE that occurs according to the FDA reporting requirement timelines. A copy of the MedWatch report will be faxed to AstraZeneca at the time the event is reported to the FDA. The investigator will compile all necessary information and ensure that the FDA receives a report according to the FDA reporting requirement timelines and to ensure that these reports are also submitted to AstraZeneca at the same time.

A cover page will accompany the Medwatch form indicating the following:

- Arimidex Investigator Sponsored Study (ISS)
- The IND number assigned by the FDA (in this study, the IND for commercial use of ESTRING will apply)
- The investigator's name and address
- The trial name and AstraZeneca Reference number

Will be sent by way of fax to: [name], Attention Arimidex ISS Safety Representative

If a non-serious AE becomes serious, this and other relevant follow-up information will also be provided to AstraZeneca and the FDA.

6. DATA MANAGEMENT

Following closure of the study, the investigator will maintain all site study records in a safe and secure location. The records will be maintained to allow easy and timely retrieval, when needed (e.g., audit or inspection) and, whenever feasible, to allow any subsequent review of data in conjunction with assessment of the facility, supporting systems, and staff.

Where permitted by local laws/regulations or institutional policy, some or all of these records can be maintained in a format other than hard copy (e.g., microfiche, scanned, electronic); however, caution needs to be exercised before such action is taken. The investigator must assure that all reproductions are legible and are a true and accurate copy of the original, and meet accessibility and retrieval standards, including re-generating a hard copy, if required. Furthermore, the investigator must ensure there is an acceptable backup of these reproductions and that an acceptable quality control process exists for making these reproductions.

The minimum retention time will meet the strictest standard applicable to that site for the study, as dictated by any institutional requirements or local laws or regulations; otherwise, the retention period will default to 15 years.

7. STATISTICAL METHODS AND DETERMINATION OF SAMPLE SIZE

7.1 Description of outcome variables in relation to objectives and hypotheses

The primary outcome variable for determining safety in this study is the number of breast cancer patients being treated with either intravaginal testosterone cream or the ESTRING for a 12 week period who have a persistently elevated serum estradiol level outside the post-menopausal range (as defined in section 3.1).

The test statistic is the number of patients that have a persistently elevated estradiol level above the post-menopausal range as described above. In the medical literature, there are no data to suggest what is “safe” or “unsafe” in terms of postmenopausal breast cancer patients being exposed to levels of estrogen above the postmenopausal range for a short duration of time (such as 12 weeks). No data exist to suggest that short term exposure to levels of estrogen above the post-menopausal range for up to 12 weeks would impact breast cancer recurrences. Therefore, it is fairly arbitrary to conclusively state that a certain rate of patients experiencing a short term increase in estradiol exposure with either of the treatment interventions (ESTRING or testosterone cream) is safe or unsafe. Taking this into consideration, we will consider each intervention “safe” if no more than 25% of patients in that arm have persistently elevated serum estradiol levels above the postmenopausal range after exposure to either of the study interventions.

The trial is designed to test the null hypothesis that a treatment is unsafe (25% or more of patients have a persistently elevated estradiol above the postmenopausal range) at a 5% level of significance. The alternate hypothesis is that a treatment is safe (i.e. fewer than 25% of patients have a persistently elevated estradiol above the postmenopausal range). Each treatment arm is tested separately. The trial is designed to have 98% power of concluding that a treatment is safe if the true failure rate is 5% and 70% power when the true failure rate is 10%.

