Up to 80 patients will be randomized to receive either testosterone or ESTRING so that 35 evaluable patients will receive each treatment. Randomization will attempt to balance the number of patients in each group based on self reported or medically documented depression, use of antidepressants, relationship status (single vs. partnered). Estradiol will be measured at baseline, at 4 weeks, and at 12 weeks into the study. If a patient is subsequently found to have a serum estradiol level outside of the post-menopausal range on day 1 of the study before the intervention begins (despite having a post-menopausal value during screening labs), this patient will be allowed to stay on study, and the subsequent estradiol level must be > 10 pg/ml higher than the baseline value to be considered a significant elevation outside the post-menopausal range. If a patient has an estradiol level outside of the post-menopausal range on the week 4 draw, or if there is a > 10 pg/ml increase in estradiol levels in patients with a baseline value above the post-menopausal range as described previously, they will have an additional lab draw at week 8.

Statistical methods

The primary outcome variable for determining safety at the end of the study is serial serum estradiol measurement. The test statistic is the number of patients that have a persistently elevated estradiol level above the post-menopausal range as described above. In the medical literature, there are no data to suggest what is “safe” or “unsafe” in terms of postmenopausal breast cancer patients being exposed to levels of estrogen above the postmenopausal range for a short duration of time (such as 12 weeks). No data exist to suggest that short term exposure to levels of estrogen above the post-menopausal range for up to 12 weeks would impact breast cancer recurrences. Therefore, it is fairly arbitrary to conclusively state that a certain rate of patients experiencing a short term increase in estradiol exposure with either of the treatment interventions (ESTRING or testosterone cream) is safe or unsafe. Taking this into consideration and after consulting with a number of breast cancer experts, we will consider each intervention “safe” if no more than 25% of patients in each arm have persistently elevated serum estradiol levels above the postmenopausal range after exposure to either of the study interventions.

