7.2 Interim Analysis / Stopping Rule

This will be a two stage study. In stage 1, ten patients are enrolled in each arm. If 3 or more of the first 10 patients in an arm fail (i.e. have a “persistently elevated estradiol level” as defined in Section 3.1 Study Design), no more patients are enrolled in that arm and it is concluded that the treatment for that arm is not safe. Patients already enrolled in that arm will be notified and given the option of discontinuing treatment. In stage 2 an additional 25 patients are enrolled in the arms that were not closed after stage 1. A treatment is considered unsafe if a total of 5 or more patients in both stages have failed (i.e. have a “persistently elevated estradiol level” as defined above). Under the null hypothesis that the treatment is unsafe with true probability of failure (i.e. persistent elevation of estradiol above postmenopausal threshold) equal to 25% or greater, the probability of rejecting the null hypothesis falsely (i.e. concluding the treatment is safe when it is not) is 5%. Figure 1 shows the operating characteristic using this two stage design.

[figure not shown]

Figure 1. Operating characteristic for two-stage safety trial.

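### The stated power and error figures do not match the protocol's own two-stage safety rule, and the 25% safety sentence is loosely worded

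*Protocol*

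**What the plan says.** **The rule.** Sections 3.3.4 and 7.2 set out the same two-stage test for each arm. Ten patients enter stage 1, and the arm closes if 3 or more fail. Otherwise 25 more are enrolled, and "A treatment is considered unsafe if a total of 5 or more patients in both stages have failed". An arm is therefore declared safe with at most 2 failures in the first 10 and at most 4 in 35.

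**The stated performance.** Section 7.1 claims "98% power of concluding that a treatment is safe if the true failure rate is 5" per cent, and 70% power at a true rate of 10%. The synopsis and section 3.3.4 give the same pair. On error, section 7.2 says "the probability of rejecting the null hypothesis falsely (i.e. concluding the treatment is safe when it is not) is 5" per cent, as does 3.3.4.

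**The 25% sentence.** Section 7.1 considers an intervention safe "if no more than 25% of patients in that arm have persistently elevated serum estradiol levels above the postmenopausal range". The synopsis (Statistical methods) has the same sentence with a small change: "if no more than 25% of patients in each arm have persistently elevated serum estradiol levels above the postmenopausal range". The next paragraph of 7.1 states the "null hypothesis that a treatment is unsafe (25% or more of patients have a persistently elevated estradiol above the postmenopausal range") and an alternative of "fewer than 25% of patients have a persistently elevated estradiol above the postmenopausal range".

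**The synopsis.** It gives the 25% sentence, both hypotheses, the 5% level and both power figures. It does not mention the two stages, the 3-of-10 stop or the 5-of-35 limit.

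**The concern.** The primary conclusion for each arm rests on this test, so its stated properties should be those of the rule actually written down. The rule is fully specified, so they can be checked exactly. They do not all agree with it.

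The wording adds to the difficulty. The sentence that defines a safe treatment speaks of a share of the patients in the arm and does not say that a true rate is meant. It also counts exactly 25% as safe, while the null hypothesis counts exactly 25% as unsafe. Someone with only the synopsis has that sentence and the hypotheses, but no count to apply. The risk is an inaccurate report of the test's power, and a careless citation of 25% as if it were the observed pass mark.

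**Working it through.** **Inputs (sections 7.1 and 7.2).** Stage 1 has 10 patients, with a stop at 3 or more failures. Stage 2 adds 25, for 35 in total. The arm is unsafe at 5 or more failures overall. The true rates considered are 5%, 10% and 25%.

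**Formula.** With X1 failures in stage 1 and X2 in stage 2, both binomial with true rate p:

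P(declared safe) = sum over x = 0, 1, 2 of P(X1 = x) × P(X2 ≤ 4 − x), where X1 ~ Bin(10, p) and X2 ~ Bin(25, p).

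**Results for the rule as written.**

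| x | p = 5% | p = 10% | p = 25% |
|---|---|---|---|
| 0 | 0.5987 × 0.9928 = 0.5944 | 0.3487 × 0.9020 = 0.3145 | 0.0563 × 0.2137 = 0.0120 |
| 1 | 0.3151 × 0.9659 = 0.3044 | 0.3874 × 0.7636 = 0.2958 | 0.1877 × 0.0962 = 0.0181 |
| 2 | 0.0746 × 0.8729 = 0.0651 | 0.1937 × 0.5371 = 0.1040 | 0.2816 × 0.0321 = 0.0090 |
| **Sum** | **0.9640** | **0.7144** | **0.0391** |
| Stated | 0.98 | 0.70 | 0.05 |

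(Sums are taken before rounding.)

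**Can another version of the rule give 98%?**

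- Without the stage 1 stop (35 patients, safe at 4 or fewer), power at 5% is 97.1%, still short of 98%. Power at 10% is 73.1%, and the false-safe probability at 25% is 4.1%.
- With the stop kept and the unsafe limit moved from 5 to 6, power at 5% is 98.3%. Power at 10% becomes 83.4%, which no longer resembles 70%, and the error at 25% becomes 8.9%, above the 5% level.

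Neither variant yields 98%, 70% and 5% together. The limit of 5 is the right one for the 5% level, since 6 breaks it. The power figure at a 5% rate is what needs correcting.

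**What does the 25% refer to?** Section 7.2 opens its error statement with "Under the null hypothesis that the treatment is unsafe with true probability of failure" and sets that probability at 25% or greater, so the 25% is a true rate. The arithmetic agrees. If 25% were the observed pass mark, up to 8 of 35 (22.9%) would be safe, since 9 of 35 is 25.7%. With the stage 1 stop kept, that gives a false-safe probability of 34.2% at a true rate of 25% and power of 92.7% at 10%, against the stated 5% and 70%. A test that rejects a true rate of 25% needs an observed rate well below it. Ignoring the two stages, the one-sided 95% exact upper limit is 24.3% for 4 of 35 and 27.7% for 5 of 35.

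**The case against.** The strongest defence is that nothing here alters a decision. The rule appears twice in matching terms. Power of 96.4% against 98% is a shortfall of 1.6 points, power at 10% is slightly understated, and the attained error of 3.9% is on the safe side of 5%, as is usual for a discrete test. The overlap at 25% is a single boundary point. Since 25% of 35 is 8.75, no count of patients can fall on it, and the formal hypotheses assign it to the null. All of this stands, and it is why the point is minor. It does not make the 98% correct: the chance of failing an arm with a true rate of 5% is 3.6%, not 2%.

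A reader might go further and infer two competing criteria, so that 5 to 8 failures of 35 would be safe under 7.1 and unsafe under 7.2. The documents do not support that. No section states an observed limit of 8. The paragraph after the 25% sentence makes 25% the null rate, tested at the 5% level, and 7.2 calls it a true probability. The stated error and power also rule out an observed 25% cut-off. With 5 to 8 failures the protocol has one outcome: the treatment is considered unsafe. Nor does 7.1 abandon error control, since it states the 5% level itself.

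**Conclusion.** Minor, but wrong as written. Under the protocol's own rule:

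- power at a 5% true failure rate is 96.4%, not 98%;
- power at 10% is 71.4%, not 70%;
- the false-safe probability at 25% is 3.9%, so 5% holds only as an upper limit.

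The 25% sentence in the synopsis and 7.1 is imprecise: it does not say that a true rate is meant, and it overlaps the null at the boundary. It does not create a second decision rule.

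The figures assume independent patients with a common failure probability, exactly 10 and then 25 evaluable patients per arm, and a clear fail or no-fail result for each. The operating-characteristic plot (Figure 1 in section 7.2) was not available, so its agreement with these values could not be checked.

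**What to change.** 1. In the synopsis and sections 3.3.4 and 7.1, restate the power as 96.4% at a true failure rate of 5% and 71.4% at 10%.
2. In sections 3.3.4 and 7.2, state the false-safe probability as at most 5% (exact value 3.9% at a true rate of 25%). Check that Figure 1 agrees.
3. In the synopsis and 7.1, replace the 25% sentence with wording such as: a true failure rate of 25% or more is regarded as unsafe; an arm is declared safe only under the rule in sections 3.3.4 and 7.2, that is, with at most 2 failures in the first 10 patients and at most 4 in 35.
4. Repeat that existing rule in the synopsis.

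The rule and the sample size stay as they are. The cost is a few sentences and a power figure at 5% that is 1.6 points lower.

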The trial is designed to test the null hypothesis that a treatment is unsafe (25% or more of patients have a persistently elevated estradiol above the postmenopausal range) at a 5% level of significance. The alternate hypothesis is that a treatment is safe (i.e. fewer than 25% of patients have a persistently elevated estradiol above the postmenopausal range). Each treatment arm is tested separately. The trial is designed to have 98% power of concluding that a treatment is safe if the true failure rate is 5% and 70% power when the true failure rate is 10%.

Secondary Outcomes

A secondary outcome variable is the change in scores on the CARES Sexual Dysfunction Subscale from baseline to week 12. The ESTRING and testosterone cream treatment groups will be analyzed independently. A paired t-statistic will be used to compare week 12 to baseline values. With 35 patients in each treatment group (ESTRING and testosterone cream), we will have 90% power to detect an effect size of 0.41 based on a two-sided paired t-test at 5% level of significance.

Another secondary outcome variable will be the difference in the mean change in CARES Sexual Dysfunction Subscale from baseline to week 12 between the ESTRING and testosterone cream treatment groups. Using a two-sample t-test, and with 35 patients in each treatment group, we would have 90% power to detect a difference of 0.57 in the change scores (e.g. a reduction of 0.1 in one group vs. a reduction of 0.67 in the other group). Currently, there is no published research to suggest an expected effect size for these interventions. However, after carrying out this trial we will have estimates for the reduction for each treatment type and could use these estimates to plan a larger study to determine if one intervention is actually superior to the other.

TABLE OF CONTENTS

Section No.	Page No.
Protocol Title Page	1
Protocol Synopsis	3
Table of Contents	6
1.0 Introduction	8
1.1 Background	8
1.2 Rationale for this study	12
2.0 Study Objectives	13
2.1 Primary Objective	13
2.2 Secondary Objectives	13
3.0 Study Plan and Procedures	14
3.1 Overall study design	14

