3.3.4 Criteria for Discontinuation

Treatment may be discontinued if subject experiences significant vaginal irritation or other side effect thought by the investigators to be related to either of the interventions.

This will be a two stage study. In stage 1, ten patients are enrolled in each arm. If 3 or more of the first 10 patients in an arm fail (i.e. have a “persistently elevated estradiol level” as defined in Section 3.1 Study Design), no more patients are enrolled in that arm and it is concluded that the treatment for that arm is not safe. Patients already enrolled in that arm will be notified and given the option of discontinuing treatment. In stage 2 an additional 25 patients are enrolled in the arms that were not closed after stage 1. A treatment is considered unsafe if a total of 5 or more patients in both stages have failed (i.e. have a “persistently elevated estradiol level” as defined above). Under the null hypothesis that the treatment is unsafe with true probability of failure (i.e. persistent elevation of estradiol above postmenopausal threshold) equal to 25% or greater, the probability of rejecting the null hypothesis falsely (i.e. concluding the treatment is safe when it is not) is 5%. The probability is 98% of concluding that the trial is safe when the true probability of failure is 5% and is 70% when the true probability of failure is 10%.

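### The stated two-stage safety rule gives 96.4% power at a true 5% failure rate, not the 98% stated; its type I error control is intact

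*Protocol*

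**What the plan says.** Section 7.1 sets up, for each arm separately and with a nominal significance level of 5%, a test of the "null hypothesis that a treatment is unsafe (25% or more of patients have a persistently elevated estradiol above the postmenopausal range"). A failure is a patient with persistently elevated estradiol as defined in section 3.1.

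Sections 3.3.4 and 7.2 give the same two-stage rule. Ten patients enter each arm, and the arm closes and is judged unsafe at 3 or more failures. If it stays open, 25 more enter, and the treatment is judged unsafe at 5 or more failures among the 35.

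Three operating characteristics are attached to this rule:

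- **Power at a 5% failure rate.** Section 7.1: "98% power of concluding that a treatment is safe if the true failure rate is 5" per cent. The synopsis (Statistical methods) gives the same 98%, and section 3.3.4 words it this way: "The probability is 98% of concluding that the trial is safe when the true probability of failure is 5" per cent.
- **Power at a 10% failure rate.** Section 7.1: "70% power when the true failure rate is 10" per cent. The synopsis and section 3.3.4 agree.
- **False-safe probability.** Section 7.2, for a true failure rate of 25% or greater: "concluding the treatment is safe when it is not) is 5" per cent. Section 3.3.4 says the same.

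Figure 1 in section 7.2 is described as the operating characteristic of this design. It is not reproduced in the text available for review.

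**The concern.** Every input needed for the operating characteristics is in the protocol, so a reader can compute them exactly, and the 98% does not come out. The protocol itself calls the choice of a safe or unsafe rate fairly arbitrary. The operating characteristics are therefore the main quantitative basis on which a reader can judge the rule, and they should be reproducible from it.

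What is at stake is small: how often a treatment with a low true failure rate would be rejected as unsafe. The decision rule, the number of patients and the protection against a false safe conclusion are not affected.

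**Working it through.** **Inputs** (sections 3.3.4, 7.1 and 7.2): stage 1 has 10 patients and stops at 3 or more failures; stage 2 adds 25; the final verdict is unsafe at 5 or more of 35. A treatment is therefore called safe when stage 1 shows 0, 1 or 2 failures and the total is 4 or fewer. The failure rates of interest are p = 0.05, 0.10 and 0.25.

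**Formula.** With X1 ~ Bin(10, p) and X2 ~ Bin(25, p) independent,

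P(safe | p) = Σ over x = 0, 1, 2 of P(X1 = x) × P(X2 ≤ 4 − x).

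**Numbers put in**

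| p | x = 0 | x = 1 | x = 2 | P(safe) | Stated |
|---|---|---|---|---|---|
| 0.05 | 0.5987 × 0.9928 | 0.3151 × 0.9659 | 0.0746 × 0.8729 | 0.9640 | 98% |
| 0.10 | 0.3487 × 0.9020 | 0.3874 × 0.7636 | 0.1937 × 0.5371 | 0.7144 | 70% |
| 0.25 | 0.0563 × 0.2137 | 0.1877 × 0.0962 | 0.2816 × 0.0321 | 0.0391 | 5% |

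(The totals come from unrounded terms.)

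**Can any stage 1 boundary rescue the 98%?** No. An interim stop for failures can only remove paths to a safe verdict. The most that a final cut-off of 4 or fewer out of 35 can give is the single-stage value P(Bin(35, p) ≤ 4), which is 97.1% at p = 0.05, 73.1% at p = 0.10 and 4.1% at p = 0.25. The 98% lies above this ceiling, so it is not a rounding of the stated rule.

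**Size of the error at p = 0.05.** The exact probability of wrongly calling the treatment unsafe is 1 − 0.9640 = 3.6%. The stated power implies 1 − 0.98 = 2.0%. The gap is 1.6 percentage points.

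**False-safe probability.** P(safe | p) falls as p rises (3.9% at 25%, 0.9% at 30%), so over all rates of 25% or more its maximum is 3.9%, at 25%. The 5% is therefore an upper bound and not the value itself.

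**Where the stated figures might come from.** A continuity-corrected normal approximation for 35 patients with the same final cut-off, Φ((4.5 − 35p)/√(35p(1 − p))), gives:

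- p = 0.05: Φ((4.5 − 1.75)/1.289) = 98.4%
- p = 0.10: Φ((4.5 − 3.5)/1.775) = 71.3%
- p = 0.25: Φ((4.5 − 8.75)/2.562) = 4.9%

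These lie close to 98%, 70% and 5%. The protocol names no method, so this is only a possible source. If it was the source, it leaves out the stage 1 stop.

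**The case against.** The strongest reply is that nothing turns on this. The two power figures are each within 2 points of the exact values and miss in opposite directions. The 70% is a round figure slightly below the true 71.4%. A 5% significance level is a ceiling that a discrete rule rarely uses in full, and 3.9% respects it. Power at a 5% failure rate remains above 96%, no decision changes, and Figure 1 may already show the exact curve.

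Most of this stands, and it limits the point to a correction of stated figures. It does not rescue the 98%. A tolerance of a couple of points suits approximate power formulas, whereas here the rule is fully given, the exact answer takes one line, and 98% exceeds what the final cut-off could reach even without an interim look. On the 5%, the significance-level wording in section 7.1 is fair. Sections 3.3.4 and 7.2 go further and state that the probability equals 5%, which is inexact.

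A reader might infer that the stated figures mix two decision rules, because moving the final cut-off to 6 or more failures gives 98.3% at a 5% failure rate. The documents do not support this. That rule would have 83.4% power at 10% and an 8.9% false-safe error, far from the other two stated figures, while the normal approximation with the protocol's own cut-off comes near all three.

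**Conclusion.** The 98% power at a true 5% failure rate is wrong as written in the synopsis and sections 3.3.4 and 7.1. The stated rule delivers 96.4%, so the chance of wrongly rejecting such a treatment is 3.6% and not 2%. The 70% at a 10% failure rate is slightly conservative (exact 71.4%). The 5% false-safe probability in sections 3.3.4 and 7.2 is an upper bound (exact maximum 3.9%), so error control holds.

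This is a minor reporting error and not a design flaw. A reader might describe the false-rejection risk as understated by almost half, since (3.6 − 2.0)/3.6 is about 44%. That ratio of two small numbers restates the same 1.6-point gap and gives it more weight than it has.

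The calculation assumes independent patients with a common failure probability within an arm, and exactly 10 and then 25 evaluable patients, each classified as failure or not. Whether Figure 1 shows the exact or the stated values cannot be judged here.

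**What to change.** Keep the rule (3 or more of 10; 5 or more of 35) and the sample size.

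- **Synopsis, 3.3.4 and 7.1:** restate the power as 96.4% at a true 5% failure rate and 71.4% at 10%.
- **3.3.4 and 7.2:** replace the statement that the false-safe probability is 5% with at most 5% (exact 3.9% at a 25% failure rate). Add the same exact value beside the 5% significance level in the synopsis and 7.1, so that all four places agree.
- **7.2:** state that the figures are exact binomial values for the two-stage rule, and check that Figure 1 passes through 96.4%, 71.4% and 3.9% at 5%, 10% and 25%.

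The cost is an edit to the text and, if needed, a redrawn figure. The stated power at a 5% failure rate becomes slightly less favourable. Enrolment, conduct and the final decision are unchanged.
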